8.3.4.1 Inclusion criteria for crossover treatment

1. With an Eastern Cooperative Oncology Group (ECOG) PS of 0-1. The criterion can be relaxed to 2 points for amputation subjects.
2. Life expectancy of ≥ 3 months.
3. All acute toxicities due to previous anti-tumor treatments or surgeries must have resolved to Grade 0-1 (as per NCI CTCAE 4.03) or to the level specified in the inclusion/exclusion criteria before C1D1 (except for toxicities such as alopecia that are deemed by the investigator as not posing safety risks to the patient).
4. With adequate organs and bone marrow functions, as defined below:

Hematology: (without blood transfusion within 14 days prior to screening, or G-CSF or other medication within 7 days prior to screening)

- Absolute neutrophil count (ANC) $\geq 1500/\text{mm}^3$ ($1.5 \times 10^9/\text{L}$);
- Blood platelet count (PLT) $\geq 100,000/\text{mm}^3$ ($100 \times 10^9/\text{L}$);
- Hemoglobin (Hb) $\geq 9 \text{ g/dL}$ (90 g/L);

Blood Biochemistry

- Serum creatinine (Cr) $\leq 1.5 \times$ upper limit of normal (ULN), or creatinine clearance (Cockcroft-Gault formula) $\geq 60 \text{ mL/min}$;
- Total bilirubin (TBIL) $\leq 1.5 \times$ ULN;
- Aspartate transaminase (AST) or alanine transaminase (ALT) $\leq 2.5 \times$ ULN; for patients with liver metastasis, ALT and AST should be $\leq 5 \times$ ULN;

Coagulation Function

- International normalized ratio (INR) ≤ 1.5 , prothrombin time (PT) and activated partial thromboplastin time (APTT) $\leq 1.5 \times \text{ULN}$;

Urinalysis

- Urine protein $< 2+$; If urine protein is $\geq 2+$, then the 24-hour urine protein must be $\leq 1 \text{ g}$;

Thyroid function

- Thyroid-stimulating hormone (TSH) $\leq \text{ULN}$; if abnormal, FT3 (T3) and FT4 (T4) levels should be examined, and the subject can be enrolled if FT3 (T3) and FT4 (T4) levels are normal.
- 5. Female subjects of childbearing potential must have a negative serum pregnancy test within 7 days prior to C1D1, and be willing to use a recognized effective contraceptive measure (such as: intra-uterine contraceptive devices, contraceptive pills, or condoms) during the study and within 3 months after the last dose of the study drug; male subjects with partners of childbearing potential must either be surgically sterilized or agree to take effective contraceptive measures during the study and within 3 months after the last dose of the study drug.
- 6. Subjects must agree and have signed the informed consent form, be willing and able to follow the scheduled visits, study treatment, laboratory tests, and other study procedures.

8.3.4.2 Exclusion criteria for crossover treatment

1. Those who have received the following treatments within 4 weeks prior to C1D1:
 - Previously received radiotherapy, surgery, immune or molecular targeted therapy for tumors;
 - Received other investigational drug of clinical studies;
 - Inoculated with a live attenuated vaccine.
2. Those who have received the following treatments within 3 weeks prior to C1D1:
3. Subjects who previously received anti-PD-1/PD-L1/CTLA4 antibodies, or VEGFR single target/multiple target inhibitors.
4. Those who plan to receive surgical treatment and/or radiation therapy for soft tissue sarcoma during the study period.
5. Presence of tumor lesions in the central nervous system confirmed by imaging diagnosis.

6. Having been treated by immunosuppressive drugs within 14 days prior to C1D1, excluding intranasal and inhaled corticosteroids or systemic steroids of physiological doses (i.e., no more than 10 mg/d of prednisolone or equivalent physiological doses of other corticosteroids).
7. Presence of any active autoimmune diseases or a history of autoimmune diseases (including but not limited to: autoimmune hepatitis, interstitial pneumonia, uveitis, enteritis, hepatitis, hypophysitis, vasculitis, nephritis, hyperthyroidism, hypothyroidism; adult patient with vitiligo or completely relieved childhood asthma may be enrolled if they do not require any intervention), or known history of allogeneic organ transplantation or allogeneic hematopoietic stem cell transplantation.
8. Complicated with severe infection (such as one requiring intravenous drip infusion of antibiotics, antifungals, or antivirals) within 4 weeks prior to C1D1, or any unexplained fever of $> 38.5^{\circ}\text{C}$ during screening/prior to the first dose.
9. Hypertension uncontrolled by antihypertensives (systolic pressure $> 140 \text{ mmHg}$ or diastolic pressure $> 90 \text{ mmHg}$).
10. Patients with clinically significant bleeding symptoms or a clear bleeding tendency within 3 months prior to C1D1, such as hemorrhage of digestive tract, stomach ulcer with hemorrhage, fecal occult blood ++ and above at baseline, or vasculitis; or arterial/venous thrombus events, such as cerebrovascular accidents (including transient ischemic attack, cerebral hemorrhage, and cerebral infarction), deep vein thrombus, pulmonary embolism, etc. within 6 months before C1D1; or requiring long-term anticoagulation therapy with warfarin or heparin, or requiring long-term antiplatelet therapy (aspirin $\geq 300 \text{ mg/d}$ or clopidogrel $\geq 75 \text{ mg/d}$).
11. Active heart diseases within 6 months before C1D1, including myocardial infarction, severe/unstable angina, etc. Left ventricular ejection fraction $< 50\%$ as revealed by echocardiography and poorly controlled arrhythmia (including QTcF interval $> 450 \text{ ms}$ in males and $> 470 \text{ ms}$ in females).
12. Having been diagnosed with any other malignancies within 3 years before C1D1, excluding adequately treated basal cell carcinoma and squamous cell skin cancer, and cervical carcinoma in situ.
13. Known allergies to the study drug or their excipients; severe allergic reactions to other monoclonal antibodies.

14. With human immunodeficiency virus (HIV) infection, or active hepatitis B (positive hepatitis B surface antigen and HBV DNA \geq 500 IU/mL) or hepatitis C (positive for hepatitis C antibody, and HCV-RNA higher than the lower limit of detection of the analytical method).
15. Presence of accompanying diseases (such as poorly controlled hypertension, severe diabetes, neurological or mental illness, etc.) or any other situation that may pose serious risks to the safety of the subjects, confuse the research results, or affect the ability of the subjects to complete the study as judged by the investigator.

8.4 Definition of End of Study

Study completion is defined as 12 months after reaching the 214 events required for the analysis of the primary endpoint (IRC-assessed PFS) or completion of collection of all OS data.

At the end of the study, all subjects who did not progress may continue treatment with the investigational drug after a new informed consent is signed. The drugs may be provided through charity donations or other forms as determined by the sponsor.

8.5 Termination or Suspension of Study

This study can be terminated early or suspended if there are sufficient reasons. This may result from the decision of the regulatory authorities, changes in comments by the Ethics Committee, efficacy or safety issues of the study medications, or the judgment of the sponsor. In addition, Hengrui reserves the right to terminate the research and development of SHR-1210 and apatinib at any time. The party who decides to suspend/terminate the study should notify the investigator, sponsor, and regulatory authorities in writing, documenting the reasons for suspension/termination. The investigator must immediately notify the ethics committee and sponsor, and provide relevant reasons.

The reasons for termination or suspension of the study may include:

- Confirmed unexpected, major, or unacceptable risk to the subjects.
- Existing efficacy data supporting study termination.
- Poor protocol compliance.
- Incomplete or undetectable measures.
- Valueless study results.

The study may continue once that issues related to drug safety, protocol compliance, and data quality have been resolved and approved by the sponsor, ethics committee, or CFDA (now NMPA).

9 COLLECTION AND PROCESSING OF PHARMACOKINETIC AND IMMUNOGENIC BLOOD SAMPLES

9.1 Collection and Processing of Blood Samples

9.1.1 Blood sampling time

Subjects receiving the combination therapy of SHR-1210 and apatinib shall undergo blood sampling for the pharmacokinetics and immunogenicity study of SHR-1210, as well as the pharmacokinetics study of apatinib.

Pharmacokinetics/immunogenicity blood sampling time points of SHR-1210: within 0.5 h pre-administration on C1D1, C2D1, C4D1, C6D1, C9D1, and every 4 cycles thereafter, with 4-6 mL of peripheral venous blood collected at each time point. If SHR-1210 medication is interrupted at the above time points, immunogenicity blood samples of SHR-1210 shall still be collected within the time windows of the corresponding time points. At 30 days after the last dose, 4-6 mL of peripheral venous blood will also be collected.

Pharmacokinetics blood sampling time points of apatinib: within 0.5 h pre-administration and 4 h (± 10 min) on C1D1, C2D1, C4D1, and C6D1, with 2 -4 mL of peripheral venous blood collected at each time point.

The time interval between the administration of apatinib on the day of blood sampling and the previous administration should be no less than 20 h. If the administration of apatinib is interrupted at the above sampling time point, there is no need to collect the blood sample related to the pharmacokinetics of apatinib.

9.1.2 Processing and storage of blood samples

Please refer to the Laboratory Manual for operation details and sample storage and transportation conditions.

9.1.3 Blood sample submission

The samples in test tubes should be sent out first in dry ice storage state. The samples in the backup tubes will be sent out after the bioanalytical laboratory confirms the receipt of the test tube samples. Details of shipping frequency and other shipping information are described in the Laboratory Manual.

10 STUDY MEDICATION

10.1 Overview of Study Drugs

10.1.1 Access to drugs

The study drugs are uniformly packaged, tested, and provided by the sponsor (see corresponding Certificate of Analysis).

10.1.2 Dosage form, packaging, and storage of study drugs

Investigational drug: SHR-1210 for injection

Manufacturer: Suzhou Suncadia Biopharmaceuticals Co., Ltd.

Dosage form: lyophilized powder.

Strength: 200 mg (proposed) in 20-mL vials.

Batch No.: see Certificate of Analysis

Route of administration: intravenous infusion.

Shelf life: 2 years (tentative) from the date of manufacture.

Storage conditions: sealed, away from light, stored at 2-8 °C in refrigerator. Do not freeze.

Apatinib mesylate tablets

Manufacturer: Jiangsu Hengrui Pharmaceuticals Co., Ltd.

Dosage form: tablet.

Strength: 250 mg/tablet; 375 mg/tablet

Batch No.: see Certificate of Analysis

Route of administration: oral administration after meals (best to take the two drugs at the same time each day).

Shelf life: 2 years.

Storage conditions: away from light, sealed, stored below 25°C.

Adriamycin hydrochloride for injection (doxorubicin)

Manufacturer: Hisun-Pfizer Pharmaceuticals Co., Ltd.

Dosage form: injection.

Strength: 10 mg

Batch No.: see Certificate of Analysis

Route of administration: intravenous infusion.

Shelf life: 24 months (tentative).

Storage conditions: kept away from light, sealed, in a cool condition (≤ 20 °C).

Cyclophosphamide for injection

Manufacturer: Jiangsu Hengrui Pharmaceuticals Co., Ltd.

Dosage form: injection.

Strength: 1 g; 0.5 g

Batch No.: see Certificate of Analysis

Route of administration: intravenous infusion.

Shelf life: 36 months.

Storage conditions: kept away from light, sealed, in a cool condition (2-8 °C).

10.1.3 Storage and stability of drugs

The investigator or his/her authorized representative (e.g. pharmacist) shall ensure that all study drugs are stored in a safe zone with qualified storage conditions and controlled access. The storage must be in compliance with regulatory requirements.

Study drugs should be stored under the storage conditions listed in Section 10.1.2. Where the protocol and other information differ, store according to the storage conditions listed on the label.

Daily maximum and minimum temperatures of all storage areas (such as freezer, refrigerator, and room temperature) must be recorded by the study center. The documented period shall begin with the receipt of the study drug until the last subject completes the last visit. Even if a continuous monitoring system is employed, a written log must be kept to ensure a correct record of storage temperature. The temperature monitoring and storage devices (such as refrigerator) should be regularly inspected to ensure proper operation.

Any deviations related to the labeled conditions on the product should be immediately reported upon discovery. The study center shall take active measures to restore the study drugs under the storage conditions described on the label, and the temperature deviation and the measures taken shall be reported to the sponsor.

Study drugs affected by the temperature deviation should be isolated temporarily and may only be used after approval by the sponsor and if it is not a protocol deviation. The use of affected investigational drugs without the approval of the sponsor is considered a protocol deviation. The sponsor will provide a detailed procedure on reporting temperature deviations to the study center.

10.1.4 Preparation of study drugs

Some drugs used in this study are administered via intravenous infusions. Therefore, the drugs should be prepared by a qualified or experienced study staff such as a study nurse. The investigational drug SHR-1210 does not contain preservatives, and must be prepared using aseptic technique. Refer to the brochure for drug preparation.

10.1.5 Administration of study drugs

SHR-1210

Administered via intravenous drip infusion at 200 mg/dose (not less than 20 min and not more than 60 min) on day 1 of each 3-week cycle for a period of up to 2 years.

Apatinib Mesylate Tablets

Administered orally at 500 mg/day once daily with warm water at approximately half an hour after meals (administration time should be the same in each day whenever possible) in 3-week cycles.

Doxorubicin

Administered via intravenous drip infusion at 60 mg/m^2 within 2 h on day 1 of each 3-week cycle. Six cycles are recommended.

If a subject has received more than 450 mg/m^2 of anthracyclines, doxorubicin will no longer be used. Doxorubicin will also be discontinued if the subject experiences a decrease in LVEF from baseline by at least 5% to an absolute value of $< 55\%$ with symptoms of chronic heart failure, or a decrease in LVEF from baseline by at least 10% to an absolute value of $< 55\%$ without symptoms or signs.

If the subject has received anthracycline treatment before the study, refer to [Appendix 3. Dose Conversion of Anthracyclines](#) for the conversion. In the course of the study, if the remaining available dose of doxorubicin (450 mg/m^2 minus the cumulative dose used previously) is $\geq 51 \text{ mg/m}^2$ (i.e., 85% of the initial dose) in a certain cycle, then the doxorubicin + ifosfamide regimen is still used this time. If the remaining available dose of doxorubicin is less than 51 mg/m^2 , the ifosfamide monotherapy regimen is used directly.

The body surface area is calculated using the Stevenson's formula: body surface area (m^2) = $0.0061 \times \text{height} (\text{cm}) + 0.0128 \times \text{weight} (\text{kg}) - 0.1529$. The final dose should be 95-105% of the calculated dose.

Ifosfamide

Combination with doxorubicin: Ifosfamide $2 \text{ g/m}^2/\text{d}$ on D1-D4, intravenous drip infusion within 4-6 h, in 3-week cycles (i.e., the total dose per cycle shall be 8 g/m^2). Six cycles are recommended.

Ifosfamide monotherapy: $2 \text{ g/m}^2/\text{d}$ on D1-D5, intravenous drip infusion within 4-6 h, in 3-week cycles (i.e., the total dose per cycle shall be 10 g/m^2). Six cycles are recommended.

If the above infusion rate is not tolerated by the subject, the investigator may consider adjusting the ifosfamide infusion rate.

The body surface area is calculated using the Stevenson's formula: body surface area (m²) = 0.0061 × height (cm) + 0.0128 × weight (kg) - 0.1529. The final dose should be 95-105% of the calculated dose.

10.1.6 Dose modifications and delay

10.1.6.1 Dose modifications for SHR-1210

Adverse events related to SHR-1210 may be immune-related (irAE), and may develop shortly after the first dose or months after the last dose. SHR-1210 should be interrupted if events listed in [Table 4](#) occur. During the study, the investigator must consult with the sponsor if, based on the benefit to risk ratio of the subject, SHR-1210 should be interrupted or resumed instead of the recommendations found in [Table 4](#) or when the situation is not listed.

When SHR-1210 is discontinued and apatinib is well tolerated, the subject may receive apatinib monotherapy.

Table 4. Criteria for SHR-1210 dose modifications

Treatment-Related Immune-Related Adverse Events (irAEs)	Severity Grades for Treatment Interruption	Resumption	Discontinuation
Diarrhea/Colitis	2-3	Recovered to Grade 0-1	Fail to resolve within 12 weeks from the last dose, or the dose of corticosteroids cannot be reduced to ≤ 10 mg of prednisone or equivalent within 12 weeks.
	4	Discontinuation	Discontinuation
AST, ALT, or bilirubin increased	2	Recovered to Grade 0-1	Fail to resolve within 12 weeks from the last dose.
	3-4	Discontinuation	Discontinuation
Hyperthyroidism	3	Recovered to Grade 0-1	Fail to resolve within 12 weeks from the last dose, or the dose of corticosteroids cannot be reduced to ≤ 10 mg of prednisone or equivalent within 12 weeks.
	4	Discontinuation	Discontinuation
Hypothyroidism	2-4	Treatment can be continued after starting thyroxine replacement therapy	Treatment can be continued after starting thyroxine replacement therapy

Treatment-Related Immune-Related Adverse Events (irAEs)	Severity Grades for Treatment Interruption	Resumption	Discontinuation
Pulmonitis	2	Recovered to Grade 0-1	Fail to resolve within 12 weeks from the last dose, or the dose of corticosteroids cannot be reduced to ≤ 10 mg of prednisone or equivalent within 12 weeks.
	3-4	Discontinuation	Discontinuation
Immune-Related Hypophysitis	2-3	Recovered to Grade 0-1; SHR-1210 treatment can be resumed after starting hormone replacement therapy	Fail to resolve within 12 weeks from the last dose, or the dose of corticosteroids cannot be reduced to ≤ 10 mg of prednisone or equivalent within 12 weeks.
	4	Discontinuation	Discontinuation
Type I diabetes mellitus (new onset) or hyperglycemia	New-onset type I diabetes mellitus or Grade 3-4 hyperglycemia accompanied with evidence of β -cell depletion	After clinical and metabolic conditions are stabilized	Continue SHR-1210 treatment.
Renal Failure or Nephritis	2	Recovered to Grade 0-1	Fail to resolve within 12 weeks from the last dose, or the dose of corticosteroids cannot be reduced to ≤ 10 mg of prednisone or equivalent within 12 weeks.
	3-4	Discontinuation	Discontinuation
Infusion reactions	2	Symptoms disappeared	Re-administer at 50% of the initial rate after symptoms resolve. If no reaction occurs within 30 min, restore the original infusion rate (100%). Closely monitor. If the symptoms recur, the administration of the current SHR-1210 dose will be discontinued.
	3-4	Discontinuation	Discontinuation
Other Treatment-Related Adverse Events	3	Recovered to Grade 0-1	Fail to resolve within 12 weeks from the last dose, or the dose of corticosteroids cannot be reduced to ≤ 10 mg of prednisone or equivalent within 12 weeks.
	4	Discontinuation	Discontinuation

Note: Treatment should be discontinued if any Grade 3 treatment-related AE recurs or any life-threatening event occurs.

For subjects with metastasis to liver and Grade 2 AST or ALT increased at baseline, treatment should be discontinued if a $\geq 50\%$ increase in AST or ALT from baseline persists for at least 1 week.

For subjects with intolerable or persistent Grade 2 treatment-related AEs, the investigator may consider interrupting SHR-1210 treatment if appropriate. For subjects with persistent Grade 2 adverse drug reactions that fail to recover to Grade 0-1 within 12 weeks after the last dose, the treatment should be discontinued.

For subjects with hypertension with a blood pressure not more than 140/90 mmHg whose AE is considered as Grade 3-4 only because of the administration of multiple antihypertensive drugs, treatment interruption is not required.

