Grade 2	Moderate reactions requiring treatment or interruption; rapidly resolve after symptomatic treatment (such as antihistamines, non-steroidal antiphlogistics, anesthetics, bronchodilators, intravenous fluids, etc.)	Intravenous administration of normal saline, 50 mg of diphenhydramine IV or equivalent and/or 325-1000 mg of acetaminophen; bedside observation and close monitoring should be given until recovery. Corticosteroids or bronchodilators can be considered based on clinical needs; The amount of study drug infused should be recorded in the original medical record; Pre-dose prophylactics are recommended for subsequent administration: 50mg of diphenhydramine or equivalent, and/or 325-1000 mg of acetaminophen can be given at least 30 minutes before the administration of SHR-1210. Corticosteroids (equivalent to 25 mg of hydrocortisone) can be used when necessary.	Interrupt. Re-administer at 50% of the initial rate after symptoms resolve. Restore the original infusion rate if no complications occur within 30 minutes. Closely monitor. If the symptoms recur, no more infusion shall be given.
Grade ≥ 3	Grade 3: Severe reaction without rapid recovery with treatment and/or interruption; or symptoms recur after alleviation; or the subject develops sequelae that requires hospitalization. Grade 4: Life-threatening.	Immediately discontinue SHR-1210; Administer normal saline by intravenous infusion. Bronchodilators are recommended. Subcutaneous injection of 0.2-1 mg of 1:1000 adrenaline solution or slow intravenous infusion of 0.1-0.25 mg of 1:10,000 adrenaline solution is recommended. Intravenous infusion of diphenhydramine 50 mg and methylprednisolone 100 mg (or equivalent dose) can be given if necessary. Medical practices and guidelines for treating allergic reactions at the study center are followed. Bedside observation and close monitoring until recovery.	Discontinuation

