13.4 Adverse Events of Special Interest

When an AE of special interest specified in the study protocol occurs, the investigator must fill out the "Report of Adverse Event of Special Interest for Hengrui's Clinical Studies" and report to the sponsor within 24 h of being notified. If the AE of special interest is also a SAE, the "NMPA Serious Adverse Event Report Form" should also be completed and submitted to the relevant authorities according to SAE reporting procedure.

- Grade ≥ 3 infusion reactions;
- Grade ≥ 3 irAEs;

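### A Grade 2 SHR-1210 infusion reaction that recurs on restart can be handled either as loss of one dose (Table 4) or as Grade 3 with discontinuation (Table 5)

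*Protocol*

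**What the plan says.** **Table 4 (Protocol 10.1.6.1), infusion reactions, Grade 2.** SHR-1210 is paused until symptoms disappear. Then: "Re-administer at 50% of the initial rate after symptoms resolve". The full rate is restored if there is no reaction within 30 minutes. If there is one: "If the symptoms recur, the administration of the current SHR-1210 dose will be discontinued".

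**Table 4, infusion reactions, Grade 3-4.** Both the resumption and the discontinuation columns read "Discontinuation".

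**Table 5 (Protocol 10.1.6.2.2), Grade 2.** The restart sequence is the same, but it ends: "If the symptoms recur, no more infusion shall be given". The row also recommends prophylaxis before later doses.

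**Table 5, Grade ≥ 3.** The grade is described as: "Grade 3: Severe reaction without rapid recovery with treatment and/or interruption; or symptoms recur after alleviation", followed by a further alternative about sequelae needing hospitalization. The management column begins "Immediately discontinue SHR-1210", and the SHR-1210 column says discontinuation.

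**Status of the tables.** Table 4 sets out criteria for dose modification, and 10.1.6.1 requires consultation with the sponsor before departing from it or when a situation is not listed. Table 5 is introduced in 10.1.6.2.2 as a set of recommendations for reference, with management to follow the practice of the study center.

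**Reporting.** Section 13.4 lists "Grade ≥ 3 infusion reactions" as events of special interest, to be reported to the sponsor within 24 hours.

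**The concern.** The event at issue is produced by the protocol's own restart instruction: a moderate reaction settles, the infusion is resumed at half rate, and the symptoms return. A site that looks for the rule finds it in two places with different consequences.

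Three things depend on which is followed: whether SHR-1210 is given again at the next cycle, whether the event goes to the sponsor within 24 hours, and how it is counted in the safety tables. SAP 5.5.2 takes the greatest CTCAE grade for an event reported more than once and summarizes events leading to treatment discontinuation. With about 30 sites, mixed handling would blur both counts. The rule applies to the investigational arm and also to control subjects who cross over, whose treatment visits follow the same section (11.4.2).

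**Working it through.** No figure in the plan is involved, so the check traces one event through both tables: a Grade 2 reaction, symptoms resolved, restart at 50% rate, symptoms recur.

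| Place | Grade under which the recurrence falls | SHR-1210 action |
|---|---|---|
| Table 4, Grade 2 row | 2 | Stop the current dose |
| Table 5, Grade 2 row | 2 | No further infusion, scope not stated |
| Table 5, Grade ≥ 3 row | 3 (recurrence after alleviation) | Discontinue |
| Table 4, Grade 3-4 row, if graded by Table 5 | 3 | Discontinue |

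**Step 1: are the two actions different?** Yes. Section 10.1.6.1 speaks of SHR-1210 being discontinued as the point after which apatinib may continue alone, that is, the end of the antibody. Stopping the current dose is narrower and leaves later cycles open.

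**Step 2: does the answer depend on the ambiguous phrase in Table 5's Grade 2 row?**
- If it means all later infusions, that row disagrees with Table 4's Grade 2 row.
- If it means only this infusion, the two Grade 2 rows agree, but both still disagree with the Grade 3 description in Table 5.

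The overlap remains under either reading.

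**Step 3: does Table 4 settle it alone?** No. Table 4 assigns actions to grades but does not describe the grades of an infusion reaction. The only such descriptions in the protocol are in Table 5. A site that grades by Table 5 and then returns to Table 4 arrives at the Grade 3-4 row and discontinues; a site that stays in the Grade 2 row stops one dose. Each can believe it is following Table 4, so nothing prompts a call to the sponsor. The note beneath Table 4 on recurrence concerns Grade 3 events that recur, and does not cover this case.

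**Step 4: range of doses at stake for one subject.**
- Upper limit: SHR-1210 every 3 weeks for at most 2 years gives 104 / 3 = 34.7, about 35 infusions.
- Illustration at the assumed median PFS of 7.0 months (Protocol 14.1), with the SAP's 30.4375 days per month and 21-day cycles: 7.0 × 30.4375 / 21 = 10.1, about 10 cycles.

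Both count from the first dose, so a reaction in a later cycle puts fewer doses at stake. The number of subjects affected cannot be calculated, because the documents give no infusion-reaction rate.

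**The case against.** **The Grade 2 rows need not conflict.** A reader might infer that Table 4 and the Grade 2 row of Table 5 flatly contradict each other. The documents do not support that. The closing sentence in Table 5 follows an instruction about a single paused infusion, and the same row foresees later doses with prophylaxis, so it can naturally be read as referring to that infusion. It is unclear wording and does not establish a contradiction on its own.

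**The Grade 3 entry opens with severe reactions.** One could read recurrence there as recurrence of a severe reaction, leaving the moderate case to the specific Grade 2 rule. That reading is available. But the criteria are separated by a semicolon and "or", so recurrence also reads as sufficient alone, and the protocol does not exclude that.

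**Table 5 is advisory and severity follows NCI-CTCAE v4.03 (12.2.2, 13.1.2).** Both are correct, and it would be wrong to treat the tables as two equally binding stopping rules. Neither point removes the difficulty: Table 5 presents its descriptions under a CTCAE grade heading, and grading by them activates the discontinuation row of Table 4 itself.

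**The event should be uncommon.** This stands. Section 5.3 describes reported reactions as low in incidence and mild, and 10.1.6.2.2 sees little potential for them. A reader might infer that sites will meet the sequence regularly, or that about 35 infusions is a typical loss; the first is unsupported and the second is a ceiling. Under every reading the infusion in progress stops when symptoms recur, so only the later doses and the reporting differ.

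**Conclusion.** The point holds as an internal inconsistency in safety instructions. The protocol's restart step leads to an event that can be classed as Grade 2 with one dose lost, or as Grade 3 with SHR-1210 ended, and the 24-hour report under 13.4 follows the class chosen. The firm part is the overlap between Table 4's Grade 2 row and Table 5's Grade 3 description; the unclear sentence in Table 5's Grade 2 row adds to it but is not needed for it.

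The conclusion assumes that a site may read recurrence as a separate Grade 3 criterion, which the punctuation allows, and may grade from the descriptions printed in Table 5. If the sponsor intended neither, the text should say so.

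The size is limited: few subjects are expected, and the effect is on later dosing, expedited reporting, and counts of Grade ≥ 3 infusion reactions and discontinuations. A reader might infer an effect on the efficacy conclusions, but the PFS analysis plan, alpha and sample size do not depend on these rows. It should be corrected because it concerns re-exposure after a repeated reaction and is cheap to settle.

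**What to change.** Reconcile the infusion-reaction rows of Table 4 with the Grade 2 and Grade ≥ 3 rows of Table 5:

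1. State one grade and one SHR-1210 action for symptoms that return when the same infusion is restarted.
2. Say whether the closing sentence of Table 5's Grade 2 row refers to the infusion in progress or to all later ones.
3. Say whether recurrence in the Grade 3 description stands alone or applies only to severe reactions.
4. Use the same grade for special-interest reporting under 13.4.

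The sponsor decides which action applies; no clinical rule is proposed here. The cost is a wording change in two tables and a notice to sites, with no added procedures or subjects.
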